#### Nifedipine ER:

- Will be started at 30 mg Qday
- As this is an ER formulation, the pill should not be divided
- Nifedipine ER will be escalated in increments of 30 mg Qday to achieve blood pressures <160/105

- Nifedipine ER dose may be divided into bid dosing for symptoms, hypotension with high doses, or hypertension between doses
- The maximum dose of nifedipine ER is 120 mg/day
- If the maximum tolerated dose of nifedipine ER is reached, labetalol may be started. If labetalol is contraindicated, or the patient is already on a maximum dose of labetalol, a third line agent such as methyldopa may be initiated (but is not supplied by the study).

#### 4.4 Participant Management

#### 4.4.1 Clinical management

A limited predefined management protocol will enhance the success of this pragmatic trial:

- A summary of the research management algorithm for patients in each of the two study groups will be strategically posted at clinic locations and will be placed in each participant's medical record; trained clinical (or research) staff will be available to measure pragmatic clinic BP at each visit.
- Routine pregnancy care at each center will be given to patients by clinical providers trained in the study protocol.

- Prescribed antihypertensive therapy according to study protocol will be supplied by the research team or designated pharmacist at each center/site until at least the time of delivery. After delivery the study medication or another appropriate antihypertensive agent will be used for at least 2 weeks after delivery.
- Prenatal visits will generally occur per local clinical standards at each site: every 1-3 weeks until 32-34
  weeks gestation when weekly or more frequent visits will be indicated (depending on antenatal testing
  initiation policy) at the discretion of the provider.
- After 20 weeks, standard clinical care suggests that preeclampsia should be excluded by a clinical diagnostic work-up (including urine protein, serum creatinine, CBC and liver enzymes as necessary) and adherence to therapy considered before enrolling patients or escalating dose due to elevated BP.
- Patients will receive lifestyle modification counseling per the routine clinical practice at each center for any
  patient with hypertension (nutrition counseling, exercise/physical activity advice and smoking and/or alcohol
  cessation interventions).
- Ultrasound for anatomy or fluid/growth and antenatal testing will be per clinical center's routine.
- Timing of delivery preferably no earlier than 38-39 completed weeks unless indicated earlier for obstetric or medical reasons according to local guidelines (consistent with ACOG recommendations)
- **4.4.2** Research management: Study personnel will monitor each participant at each clinic visit (in person or remotely) to review the treatment plan based on the pragmatic clinic BP. This pragmatic clinic BP will be based on the usual clinic BP (single BP <140/90 or repeat BP measurement if ≥140/90. If the pragmatic clinic BP is elevated above the threshold that warrants treatment adjustment (≥140/90 for active arm and ≥160/105 for standard comparison group), the provider will take medication adherence into consideration to determine if any changes in study medications or doses are indicated. Study personnel will dispense additional medication as needed per study protocol. At scheduled clinic visits, participants will be asked about adherence to the medication regimen and off-study BP medications. If the participant's response to this question indicates a possible problem with adherence, and the participant is not at the appropriate BP target, this will be taken into consideration in dose adjustments.

Either clinic or study personnel will measure seated BP and heart rate at each clinic visit after a rest period using the routine clinical procedures.

#### Management of patients intolerant of treatment regimen

• For adverse effects such as hypotension (maternal BP<90/60) and persistent dizziness, headaches, lightheadedness or fatigue and no other potential cause other than the medication, dividing the current dose into more frequent doses will be used (e.g. tid instead of bid for labetalol and bid instead of daily for nifedipine ER) consistent with FDA recommendations. If this does not help the next step will be to reduce the daily dose of the medication to keep the BP ≥ 90/60 before switching to an alternative medication.

For major reactions such as an allergic reaction to the first line medication, it will be discontinued and
replaced with the alternate first line medication. If both labetalol and nifedipine are contraindicated, other
acceptable medications such as methyldopa will be prescribed at the discretion of the clinical provider. The
patient will still be followed by the study in an intent-to-treat fashion.

#### Adherence to antihypertensive medications will be assessed as follows:

- a) The clinical provider (with the help of study staff as applicable) will assess adherence according to usual clinical routine to determine whether the participant has been adherent within the past 24 hours. For example, the provider could ask "When was the last time you took your medication? "Do you take your medication every day?" The provider will use this information to determine whether to titrate the BP medication dose(s) as clinically indicated.
- b) At clinic visits when the patient requires a medication refill, study staff will conduct a pill count of the patient's study medication and record it. This will be used to estimate adherence. Given the pragmatic nature of the study, a more elaborate plan to monitor adherence will not be implemented by the research team.

All participants will be probed about off-study use of antihypertensive medication(s), alternative medications, and other vasoactive drugs during the clinic visit. Appropriate sources of this information include participant (or significant other) report, current pharmacy action profiles, and verification of medications documented in the medical record.

In the standard comparison group, labetalol treatment will be started only for BP ≥160/105. Only the lowest dose needed to give keep BP below this level will be given. Methyldopa or other clinically acceptable medication at the discretion of the clinical provider will be the third-line medication (after maximum tolerated doses of both labetalol and nifedipine ER) in the unlikely situation that a third medication is needed.

#### 4.5 Participant follow up

Research nurses trained and highly experienced in obstetric and perinatal outcomes abstraction at each center will be responsible for research data abstraction from patient medical records. Outcomes will be ascertained until delivery and maternal/infant discharge. At hospital admission for delivery, maternal blood will be collected at the time of the admission lab work and will be processed for whole blood, plasma and serum samples. At delivery, cord blood will be collected and processed for future studies. These will include a comprehensive assessment of the role and interactions of clinical, biological and biophysical factors (e.g., BP levels, maternal obesity, smoking, glucose intolerance, hyperlipidemia, genes/pharmacogenetics and ultrasound findings) on the occurrence and severity of adverse outcomes including preeclampsia and fetal growth restriction. The placenta will be collected as part of clinical routine and sent to hospital pathology lab for sampling and analysis. Specimens will be frozen and shipped in batches to the UAB Ob/Gyn Diagnostic and Research Lab for storage.

After hospital discharge, participants will be followed up postpartum at 6 (4-12) weeks to ascertain maternal and infant status including readmissions and ER or unscheduled visits. The records of any ER visits or hospitalizations will be obtained for review.

In the active treatment group, the goal blood pressure will remain <140/90 for at least two weeks postpartum. The selection of medication may be based on clinical history, prepregnancy regimen and providers' preference. Participants in the standard care per ACOG (no treatment) arm may be initiated on antihypertensive therapy postpartum per their primary provider; choice of antihypertensive is left to their provider. CHAP will provide study medication when treatment is per protocol (i.e. prescription for labetalol or nifedipine to achieve blood pressure <140/90 for active treatment; prescription for labetalol or nifedipine to achieve blood pressure <160/105 for no treatment arm). The follow-up assessment will include items to assess adherence to antihypertensive therapy since delivery.

It is anticipated that by the end of the postpartum period most patients will be continued on labetalol or nifedipine ER, resume taking their usual prepregnancy medication, or be started/continued on an appropriate BP medication regimen by their clinical provider, taking into consideration their BP, co-morbidities, medication cost and future plans. Postpartum adherence, BP control and intervening clinical visits will be assessed by the study team at the 6 (4-12) week follow up visit.

Longer follow-up is anticipated as part of a separate follow-up study for which funding will be sought. This may include an interim phone visit at 6 months and in-person visits at 5 years to ascertain long-term maternal and child outcomes.

#### 4.6 Adverse event reporting

The CHAP trial is testing whether antihypertensive medication used in pregnancy to maintain BP <140/90, compared with ACOG recommendation (no treatment), for uncomplicated mild CHTN reduces the frequency of important adverse outcomes associated with CHTN including 1) a severe composite outcome (perinatal death, placental abruption, severe preeclampsia and indicated preterm birth <35 weeks) and 2) SGA - a safety outcome. It is not a study of specific anti-hypertensive agents. The antihypertensive agents provided by the trial have been approved by the Food and Drug Administration (FDA), are routinely prescribed for lowering BP and are commonly used in pregnant women as part of clinical routine to treat BP when indicated.

Patient safety will be carefully monitored. Each participating investigator has primary responsibility for the safety of the individual participants under his/her care. In addition, an independent Data and Safety Monitoring Board (DSMB) will have primary responsibility for monitoring the accumulating study data for signs of adverse trends in morbidity/mortality and treatment-related serious adverse events. The DSMB will be appointed by the sponsor (NIH/NHLBI) and will comprise clinical scientists with expertise in Statistics/Epidemiology, Obstetrics, Neonatology and Internal Medicine/Cardiology.

An adverse event (AE) is defined as any untoward or unfavorable medical occurrence in a human subject, including any clinically significant abnormal sign (for example, abnormal physical exam or laboratory finding), symptom, or disease, temporally associated with the subject's participation in the research, whether or not considered related to the subject's participation in the research. Sites will report all serious SAEs and selected AEs to the Data Coordinating Center.

Consistent with NHLBI guidelines and OHRP policy, SAEs are adverse events that meet any of the following criteria:

- · fatal or life-threatening
- · result in significant or persistent disability,
- require or prolong hospitalization,
- · result in a congenital anomaly/birth defect, or
- are important medical events that investigators judge to represent significant hazards or harm to research participants.

Specifically, any AE that meets any of these criteria (maternal death, ICU admission stroke, myocardial infarction, cardiomyopathy; fetal death or neonatal death) will be documented and reported as an SAE. SGA as a study outcome will also be a monitored AE, but not reported as an SAE, as these will be determined using appropriate birth weight and GA curves. In addition, any unexpected event which the investigator believes to have been caused or contributed to by the intervention, regardless of whether it resulted in hospitalization, will also be considered an AE or SAE (e.g., severe allergy or anaphylaxis suspected to be due to the patient's BP medication). Other AEs include maternal bradycardia, hypotension (BP< 100/60), syncope, stroke, renal failure, heart failure and may include neonatal hypoglycemia, hypotension and bradycardia unrelated to prematurity or diabetes mellitus.

Participants will be queried for SAEs and selected AEs at each prenatal clinic visit and patients admitted to the hospital will be monitored for these events.

## 4.7 Study Outcome Measures and Ascertainment

#### 4.7.1 Primary outcomes:

- 1. A composite outcome (Effectiveness) including at least one of:
  - a) Fetal or neonatal death.
  - b) superimposed preeclampsia with severe features up to two weeks postpartum;
  - c) placental abruption, or
  - d) indicated PTB <35 weeks (i.e. not due to spontaneous preterm labor or membrane rupture).

The definition of preeclampsia with severe features is as follows:

- a) Worsening HTN ≥160/110 after 20 weeks' gestation and proteinuria OR (in the absence of proteinuria);
- b) Worsening HTN above prior baseline (≥140/90) AND [cerebral (including seizures or persistent headaches) or persistent visual symptoms OR thrombocytopenia <100,000 OR creatinine≥1.2 mg/dL (or doubling from baseline), OR 2-fold elevated liver enzymes or HELLP syndrome OR persistent right upper quadrant pain OR pulmonary edema (including oxygen desaturation <90% requiring treatment with diuretics and oxygen)].

To be included in the primary outcome, abruptio placenta is defined as greater than usual uterine bleeding in the absence of placenta previa or trauma (associated with contractions, non-reassuring fetal heart tones and/or clinical diagnosis of abruption) leading to delivery. Other cases of "abruption" will be collected but not included in the primary outcome.

This primary outcome drives all key sample size considerations. This composite outcome is a measure of severe outcomes related to preeclampsia or CHTN; similar outcomes have been used in other trials, including the NICHD MFMU CAPPS and High Risk Aspirin trials. Outcomes will be adjudicated through an independent centralized review familiar to our group.

2. Poor fetal growth (i.e. SGA<10th percentile based on birth weight): We will also examine SGA <5th percentile. SGA is not included in the composite because of concerns that therapy may be a cause (impaired placental blood flow). This is the primary safety outcome to evaluate harms. Based on our preliminary data, however, BP control may be associated with a reduction in risk of SGA. A national standard weight curve such as Alexander's or any other acceptable customized curve will be used to identify SGA infants.

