#### 2. Systematic reviews:

i. A single systematic review (7 trials in 623 women) focused solely on antihypertensive therapy in pregnant women with CHTN (excluding gestational hypertension or preeclampsia) at baseline. The results are depicted in Figure 1. The observed reduction in severe hypertension in treated patients was not accompanied by significant reductions in key adverse pregnancy outcomes. Results for indicated preterm birth, which is the specific type of preterm birth associated with CHTN, were not available.

ii. A Cochrane review included 4282 women with CHTN as well as gestational HTN or preeclampsia who were enrolled in 46 small trials of antihypertensive therapy. Overall, antihypertensive treatment with any drug versus no treatment/placebo lowered the incidence of severe HTN (RR 0.5; 95% CI 0.41-0.61). There were no significant differences between treatment groups in preeclampsia (0.97; 0.83-1.13), eclampsia (0.34; 0.01-8.15), perinatal death (0.73; 0.50-1.08), PTB (0.98; 0.85-1.13), SGA (1.04; 0.84-1.27), abruption (1.83; 0.77-4.37) or maternal death. There were reductions in fetal loss (0.39; 0.17 - 0.93) and in neonatal respiratory distress syndrome (0.28; 0.12- 0.63) with treatment.

Methyldopa alone versus no treatment was associated with a lower incidence of fetal or neonatal death (0.35; 0.13 - 0.94). Analyses restricted to women with CHTN yielded similar results but corresponding data for fetal loss and respiratory distress were not available. Use of a placebo in the control group did not influence results. Considering the limited size and flaws of the individual trials (particularly combining patients with disparate types of hypertension), the authors concluded that:

- i. it remains unclear whether anti-hypertensive therapy for mild CHTN in pregnancy is worthwhile; and
- ii. larger trials are needed to provide reliable data on the benefits and harms of treatment for mild CHTN in pregnancy. Importantly, women with CHTN at baseline are distinctly different from those with gestational hypertension or preeclampsia, and perhaps more likely to benefit or suffer harm from therapy, and therefore should be studied separately.

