#### 3.3 Design Summary

This study is a multicenter randomized controlled clinical trial of 2404 women with randomization stratified by center (Figure 2). Patients with mild CHTN (based on pragmatic clinic BP measurements <160/105) will be randomized to either treatment with a first-line antihypertensive agent recommended by ACOG (labetalol or nifedipine ER supplied by the study) or other provider preferred medication (not supplied by the study), or no anti-hypertensive treatment. Consistent with the pragmatic design to evaluate the policy of therapy and not a specific medication, rarely, women who have a strong preference for their own established medication (e.g. intolerance of other medications) will be included in the study (and will use their own supply).

For participants in the active treatment group, labetalol dose, nifedipine ER dose or other antihypertensive medication dose will be escalated as needed to achieve target BP (<140/90). Dosing frequency may be increased to tid in order to control BP or to reduce side-effects. If the maximum tolerated oral dose of the first line agent is reached and BP is not at target, 2nd line treatment (labetalol or nifedipine ER) will be initiated to achieve the target BP. After delivery, goal BP will be <140/90 for at least two weeks.

In the comparison group, treatment will not be started if BP remains <160/105; for BP ≥160/105, treatment with a first line agent (labetalol or nifedipine ER) will be initiated and maintained at the lowest dose needed to keep BP <160/105. Goal BP after delivery will follow usual practice at each site.

Analysis will be by intent to treat.

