## 4.7.2 Major secondary outcomes

- 1) Composite maternal cardiovascular and other morbidity: Death, any new heart failure, stroke or encephalopathy, Ml/angina, pulmonary edema, ICU admission/intubation, encephalopathy, or renal failure.
- 2) Persistent severe maternal hypertension (with or without proteinuria) + components of the primary composite endpoint
- 3) Preterm birth and Indicated preterm birth (<37 weeks)
- 4) Composite of severe neonatal morbidities: Bronchopulmonary dysplasia (BPD), Retinopathy of prematurity (ROP), Necrotizing enterocolitis (NEC), Intraventricular hemorrhage (VH) grade III/IV.

The following outcomes will be evaluated in secondary studies:

- 5) Timing of delivery outcomes: The risks of 3 key outcomes, a) perinatal death, b) composite neonatal morbidity and c) composite of severe maternal morbidity (defined above) will be examined in relation to gestational age (completed weeks from 36 to 40 weeks) using longitudinal analysis methods to determine the delivery gestational age at which risks nadir (see analysis section).
- 6) Biospecimen collection: i) Maternal whole blood, plasma, paxgene and serum at the time of randomization and midtrimester (24-30 weeks), ii) cord blood (whole blood, serum and plasma) at time of delivery, iii)

- placenta collected and sent to pathology for routine clinical evaluation. All maternal and cord blood specimens will be frozen at -80 degrees C for future studies.
- 7) These future biospecimens studies will include a comprehensive assessment of the role and interactions of clinical, biological and biophysical factors (e.g., BP levels, maternal obesity, smoking, glucose intolerance, hyperlipidemia, genes/pharmacogenetics and ultrasound findings) on the occurrence and severity of preeclampsia, SGA and other outcomes.
- 8) Adherence to treatment at 6 (4-12) weeks postpartum: The follow-up questionnaire will include items to assess adherence to antihypertensive therapy since delivery.

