#### 4.7.3 Other maternal outcomes

- 1. Superimposed Preeclampsia (mild or severe including eclampsia)
- 2. Superimposed gestational hypertension (persistent hypertension above baseline without proteinuria occurring after 20 week's gestation).
- 3. Serial maternal systolic and diastolic BP (mean values and changes during pregnancy should differ between groups if the intervention is successful). Both the pragmatic clinic and standardized automated/Omron BPs will be assessed.
  - 4. Severe hypertension (treatment needed)
  - 5. Cesarean delivery
  - **6.** Blood transfusion (during pregnancy or postpartum)

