#### 5.1.1 Original Sample Size

We used data from the MFMU Network's High Risk Aspirin study (enrollment into the CHTN group was based on pragmatic clinic BPs) to estimate the frequency of the composite outcome components among 763 women with mild CHTN at baseline as follows: Fetal or neonatal death = 6.16%; severe preeclampsia (severe hypertension and proteinuria, eclampsia, preeclampsia with thrombocytopenia, creatinine>1.4, elevated liver enzymes) =0.66%; abruption =1.46%; indicated PTB <35 weeks =12.32%. The frequency of the primary composite outcome was 16%. Assuming a 2-sided alpha of 0.05 and conservative baseline incidence of 16% (since this is regardless of BP lowering therapy, and we expect the incidence to be higher in those not receiving therapy) the unadjusted sample sizes/arm needed to detect a 20-30% reduction in the primary outcome with 85-90% power are presented in Table 5. These unadjusted estimates do not take into account drop-ins and drop-outs or the interim look we propose. We assume: the 10% of the control group that will require treatment for severe hypertension are already well-accounted for in our baseline rate of 16% estimated from usual care; that in addition there will be up to a 10% rate of protocol violations (treatment in the control group without meeting criteria for severe hypertension) and that nonadherence in the treatment arm is 10%. The adjusted outcome rates for 25% reduction are: 15.6% and 12.4%, and the revised adjusted sample sizes/arm accounting additionally for 8% loss-to-follow up are presented in Table 5.

Table 5: Estimated sample size/arm (30%, 25% and 20% Reductions) under original plan

	30% REDUCTION		25% REDUCTION		20% REDUCTION	
Power	Unadjusted	Adjusted	Unadjusted	Adjusted	Unadjusted	Adjusted
90%	1075	1829	1587	2696	2539	4314
85%	919	1561	1356	2305	2170	3687

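### Read literally, the severe-preeclampsia definition in the primary composite excludes a woman with proteinuria and an organ or symptom feature at 140-159/90-109, although the same woman without proteinuria counts; the effect is small

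*Combined protocol and SAP*

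**What the plan says.** Protocol 4.7.1 makes severe preeclampsia one of four components of the primary composite and defines it in two limbs.

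- Limb (a): "Worsening HTN ≥160/110 after 20 weeks' gestation and proteinuria OR (in the absence of proteinuria", where the closing parenthesis leads into limb (b).
- Limb (b): "Worsening HTN above prior baseline (≥140/90) AND [cerebral (including seizures or persistent headaches) or persistent visual symptoms OR thrombocytopenia <100,000", followed by creatinine, liver, right-upper-quadrant pain and pulmonary edema criteria.

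The same section says of the composite: "This primary outcome drives all key sample size considerations".

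Two other protocol sections bear on the reading.

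- Section 5.1.1 gives the component behind the 16% baseline, as a percentage: "severe preeclampsia (severe hypertension and proteinuria, eclampsia, preeclampsia with thrombocytopenia, creatinine>1.4, elevated liver enzymes) =0.66". It puts no proteinuria restriction on eclampsia or the organ features.
- Section 4.7.2 shows how the protocol writes a criterion to which proteinuria is irrelevant: "Persistent severe maternal hypertension (with or without proteinuria) + components of the primary composite endpoint".

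SAP 3.1.1 names the severe-preeclampsia component without defining it. It points to the protocol's definition for abruption only.

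**The concern.** Under the literal text, proteinuria takes a woman out of limb (b). If her pressure stays below 160/110 she cannot enter through limb (a) either. So a sign of preeclampsia turns an event into a non-event, and the counting rule departs from the rule behind the planning rate.

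The exclusion is also not obviously neutral between arms. For women with proteinuria and a feature, the literal rule counts the event only if BP reaches 160/110. The arms differ by BP strategy: the Lower BP arm is treated to below 140/90, whereas "In the comparison group, treatment will not be started if BP remains <160/105". The protocol's own background expects treatment to reduce severe hypertension: "antihypertensive treatment with any drug versus no treatment/placebo lowered the incidence of severe HTN (RR 0.5; 95% CI 0.41-0.61". Some of that BP effect would be recorded as a difference in preeclampsia events, in favour of the Lower BP arm. The composite is also the outcome used in the sample size reassessment on the first 800 women and tested at the interim look.

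**Working it through.** **1. Truth table.** The permissive reading lets limb (b) apply whatever the proteinuria status. With BP below 140/90 all four combinations are non-events under both readings. The other eight:

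| BP | Proteinuria | Feature | Literal | Permissive |
|---|---|---|---|---|
| 140-159/90-109 | no | no | no | no |
| 140-159/90-109 | no | yes | event | event |
| 140-159/90-109 | yes | no | no | no |
| **140-159/90-109** | **yes** | **yes** | **no** | **event** |
| ≥160/110 | no | no | no | no |
| ≥160/110 | no | yes | event | event |
| ≥160/110 | yes | no | event | event |
| ≥160/110 | yes | yes | event | event |

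The readings differ in one of 12 cells.

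**2. The plan's own sample size.** Inputs (protocol 5.1.2, SAP 3.1.4): 16% baseline, 33% reduction, so 10.72%; two-sided 0.05; 85% power; 10% noncompliance and 10% crossover; 5% attrition. With n = [1.96√(2p̄q̄) + 1.036√(p₁q₁ + p₂q₂)]² / (p₁ − p₂)²:

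- Undiluted: 745 per arm (stated 748).
- Diluted rates: 0.9×16 + 0.1×10.72 = 15.47%, and 0.9×10.72 + 0.1×16 = 11.25%. This gives 1164 per arm (stated 1142, a 1.9% gap).
- Attrition: 1142/0.95 = 1202.1, so 1203 rounded up (stated 1202).

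The figures reproduce and the wording issue does not change them.

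**3. Critical difference at the final look.** Boundary χ² > 3.87; mean diluted rate 13.36%; 1142 per arm.

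√3.87 × √(2×0.1336×0.8664/1142) = 1.967 × 0.01424 = 2.80 percentage points, or 32 events.

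**4. How many women could be affected.** The documents give no rate for the disputed cell. Two rates for severe preeclampsia as a whole, both from the High Risk Aspirin trial, are available:

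- Protocol 5.1.1: 0.66%. The other components sum to 6.16 + 1.46 + 12.32 = 19.94%, more than the 16% composite, so overlap is certain. Women counted through severe preeclampsia alone are between 0 and 0.66% (0 to 16 of 2404).
- Protocol 2.7.3, Table 2: (478×1.9 + 221×5.9 + 60×1.7)/759 = 3.05% (at most about 73 of 2404).

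**5. Spurious arm difference.** Let x be the percentage of women with proteinuria plus a feature and no other component, assumed equal in both arms. Let s be the share of them reaching 160/110 in the Standard arm (assumed 0.3 to 0.7). Let r be the Lower/Standard ratio for reaching it: 0.50 from the Cochrane review, 27.5/40.6 = 0.68 from CHIPS, both assumed to carry over to this subset. The literal rule counts x·s in Standard and x·s·r in Lower, so the spurious difference is x·s·(1 − r).

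| x | s = 0.3, r = 0.677 | s = 0.7, r = 0.50 |
|---|---|---|
| 1% | 0.097 points | 0.35 points |
| 0.66% | 0.06 points | 0.23 points |
| 3.05% | 0.30 points | 1.07 points |

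To reach 2.8 points unaided, x would have to be 2.8/0.35 = 8.0% at the least favourable inputs, or 2.8/0.097 = 28.9% at the other end.

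**6. Power.** If the literal rule removed x points from the 16% rate at the same 33% reduction, power at 1142 per arm would fall from 84.3% (x = 0) to 83.0% (0.5), 81.6% (1.0) and 75.1% (3.0). On the 0.66% rate the loss is about 2 points. The last figure would need nearly every severe case in the Table 2 data to be excluded. Protocol 5.1.2 also reports an overall event rate above expectation, so this is chiefly a classification issue.

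**The case against.** The best reply is that the parenthesis means proteinuria is not required for what follows, rather than that its presence disqualifies. That is probably the intention. The planning definition supports it, and excluding a woman with a seizure because she has proteinuria makes little sense. SAP 3.1.1 also provides two masked adjudicators who must agree, with a third if needed. The manual of operations and form HP18, neither of which is among the documents, may state the rule. All of this stands and limits the practical risk, but the only definition in the documents still says something else, and masked review does not tell adjudicators which reading to apply.

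The sizing is also open to challenge. The share s is assumed, and the ratios describe severe hypertension in broader populations, not women who already have proteinuria and an organ feature. That is correct: step 5 shows direction and order of magnitude only. The current definition also lists more features than the planning one, so neither 0.66% nor 3.05% strictly bounds the trial's own rate.

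A reader might infer three stronger things that the documents do not support.

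- That these women drop out of the composite altogether. They still enter through indicated preterm birth before 35 weeks, abruption, or fetal or neonatal death.
- That they would appear elsewhere only as non-severe cases. The outcome in protocol 4.7.3, "Superimposed Preeclampsia (mild or severe including eclampsia", is undivided, and several limb (b) features overlap the maternal morbidity composite in 4.7.2.
- That the death component is contradictory. SAP 3.1.1 counts deaths within 28 days, while protocol 4.7.6 ascertains neonatal death to 90 days in undischarged newborns. One is an event definition and the other a collection period. A clarifying sentence would help, but this is not part of the finding.

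**Conclusion.** The definition is wrong as written, with a small effect. Followed literally, it misclassifies one well-defined group in the primary endpoint, conflicts with the planning definition in protocol 5.1.1, and is not repaired by the SAP or by any other section of the documents.

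The number of women affected cannot be derived. Treating every severe-preeclampsia case as having proteinuria, a feature and no other component gives about 0.1 to 1.1 points of spurious difference across the two source rates, against about 2.8 points needed for significance. This rests on the assumed s, the transferred r, and equal x in both arms. The direction would tend to favour the Lower BP arm. The issue could matter for a result near the boundary; it could not plausibly create a significant result alone.

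Nothing in the documents shows that adjudicators applied the literal reading, so it would be wrong to conclude that events have been miscounted.

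**What to change.** Before unblinding:

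1. In protocol 4.7.1, delete the parenthetical condition at the end of limb (a), and state inside limb (b) that it applies with or without proteinuria. Limb (a) should stay as 160/110 or above together with proteinuria. Simply swapping the phrase where it now stands could be misread as admitting 160/110 without proteinuria, which overlaps a separate outcome in 4.7.2.
2. In SAP 3.1.1, cite the protocol definition for this component, as is already done for abruption.
3. Align form HP18, and confirm under masking that cases already adjudicated, including those among the first 800 women, followed this rule. If the manual or HP18 already states it, copy that text into the protocol.

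Cost: no new visits or data collection. Under protocol 1.4 the wording change needs Steering Committee and IRB approval, and DSMB approval if it is judged a major change. A masked re-check of disputed-cell cases may be needed. Its size is unknown, because the documents do not show whether HP18 records BP, proteinuria and features separately.
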